15 STATISTICAL CONSIDERATIONS

15.1 Study Design and Conduct

A total of 70 patients may be consented on the main informed consent, in order to randomize a sufficient number of patients with newly diagnosed GBM who completed standard of care radiotherapy with temozolomide into one of two treatment arms. Patients will receive 3 bi-weekly (every other week) vaccinations during the first cycle of either: (Arm 1) 5-day standard of care temozolomide at 150-200 mg/m²/day, or (Arm 2) 21-day temozolomide at 75-100 mg/m²/day post chemo-radiation (please refer to study overview for timing of vaccine administration). We will target the treatment of 26 patients (13 per arm) who are evaluable for the primary immune endpoint. All patients will continue to receive PEP-CMV vaccine as described in the Treatment Plan at 4 (+2) week intervals for up to 20 vaccines, these vaccine administrations will coincide with TMZ cycles for those who are receiving TMZ.

With the 20190312 protocol amendment, the study's primary analysis has focused on patients who receive Component A only. Hence, we target the treatment of 26 patients (13 per arm) who received only Component A and are evaluable for the immune endpoints.

Once 6 subjects have been accrued to each arm of this study and the last patient has received the third vaccination and has been followed for approximately 2 weeks, toxicities up to that point will be formally monitored. Further accrual will be dependent upon the prevalence of unacceptable toxicity within each arm. See Section 15.4 for further details of monitoring guidelines.

Following the safety events of vaccine reactions that were initially reported on 20170407, the study was amended to investigate, in a separate unrandomized drug safety cohort of 6 patients, the etiology of these events. Within this cohort, patients were consented to receive study vaccine with standard of care (SOC) 5-day TMZ at 150-200 mg/m²/d for 28-day cycles with various sequences of vaccine components A and B. Details of this safety assessment plan are provided in Section 11.4.3. Upon completion of this unrandomized portion of the study, the randomized study was allowed to reinitiate with changes to vaccine administration procedures based on observations made in the safety cohort (protocol v. 20180719). Subsequently, Component B was removed from the vaccine for future patients due to problems with availability and supply (protocol v.20181218). On 20190130, Component B was removed from the vaccine for all patients (current and future) due to two new safety events observed and reported in January 2019.

As of 20190312, 13 patients have been enrolled on the study:

Periods of Study Conduct	Patient Enrollment Description as of 20190312
Initial – Randomized	3 patients randomized and treated with 1-2 vaccinations that included Component A and B as originally planned before study suspension: 
• 2 patients assigned to standard TMZ on days 1-5• 1 patient assigned to dose-intensified TMZ on days 1-21
Safety Cohort (See Section 11.4.3)	6 patients treated with standard TMZ with different sequences of Component A and B
Resumed – Randomized	Once randomization resumed, the 1 st 4 patients randomized:

	
• 2 patients assigned to standard TMZ with vaccine that included Component B; Component B was dropped for these 2 patients due to safety events (one patient received only one vaccine containing Component B, and the other patient received 3 vaccines containing Component B).• 2 patients assigned to dose-intensified TMZ – Component B was dropped before these patients started treatment; hence, only Component A was part of vaccine. 
For all subsequent patients enrolled, the vaccine includes Component A only.

--	---

As of protocol version 20190312, the primary analysis of this study will focus on only those patients who receive Component A alone.

As of 20200110, 15 patients have received only Component A of which 8 are currently evaluable for the immune response primary endpoint.

15.2 Sample Size Justification for Immunologic Response Outcome

Of primary interest is a comparison of the 2 arms with respect to the peak immune response (ELISPOT) in the immune monitoring blood that will be collected as described in the treatment plan. A patient will be considered evaluable and included in these analyses if the patient had their immune monitoring blood work drawn prior to initiation of post-RT TMZ cycle 2, if applicable.

Given that humoral responses are known to be surrogates for cellular immune responses (ELISPOT), we will use antibody titer data from the ACT II study, a study conducted at Duke, to estimate an appropriate sample size for pairwise comparison of peak immune response (ELISPOT). The ACT II dataset provides peak antibody titer to EGFRvIII data for 5 patients in arm A and 10 patients in arm B. Given that the distribution of peak titers in the two arms is not normally distributed, resampling methods were used to estimate the power of a comparison using a one-tailed Wilcoxon rank sum test. The median peak titer (and range) in arm A and B were 51200 (2560 – 204800) and 385000 (20480, 20480000) respectively. Each of 10000 simulations for a fixed sample size per arm involved randomly sampling with replacement the peak antibody data separately within arm A and B, and then computing the Wilcoxon rank sum test. The percentage of tests that was statistically significant estimated the power of the statistical test. With 2 primary endpoints, power calculations assumed a type I error rate of 0.025. With 13 evaluable patients in each arm, there is 81% to detect a difference similar to that observed in ACT II. In order that there are 26 evaluable patients, we anticipate a need to consent up to 70 patients on the main informed consent form.

With the 20190312 protocol amendment, the study has focused on patients who receive Component A only. Hence, we target the treatment of 26 patients who have received only Component A and are evaluable for the assessment of immunologic response. As of 20200110, 15 patients have received only Component A of which 8 are evaluable for immune response.

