--	---

	
tachycardia, of any duration will be considered an unacceptable toxicity. Although not considered an unacceptable toxicity, any patient with \geq Grade 2 urticaria will not receive further vaccines, will be withdrawn from the study, and will be replaced if less than 3 vaccines have been administered without unacceptable toxicity. The prevalence of unacceptable toxicities occurring during the initial 3 bi-weekly vaccinations or the vaccinations administered concurrently with temozolomide will be continuously monitored. If more than 25% of accrued patients experience unacceptable toxicities, then accrual will be suspended and reported toxicity will be carefully reviewed to determine if modifications to the protocol treatment should occur. Peptide vaccinations employing Montanide ISA-51 as adjuvants have generally been well-tolerated in human patients in numerous phase I-III trials.
 
Treatment Plan: Patients will be vaccinated in conjunction with subsequent 28-day cycles for a total of 6 to 12 adjuvant TMZ cycles after RT if patient is continuing on TMZ (i.e., for patient's who's tumor is methylated or the status is inconclusive). Cycles are every 4 (+ 2) weeks, adjusting for slight delays on startup or scheduling of each 28-day cycle. For patients whose tumor is methylated or the status is inconclusive, the total number of TMZ cycles given will be at the discretion of the treating oncologist. During the 28-day cycles, vaccinations will occur on day 23 (-1 day, + 2 days) of each cycle for each arm: (Arm 1) standard TMZ (200 mg/m²/day on days 1-5 of each 28-day cycle), or (Arm 2) dose-intensified TMZ (100 mg/m²/day on days 1-21 of each 28-day cycle).
 
All vaccines will be given i.d. approximately 10 cm below the inguinal ligament bilaterally. Component A will be administered half in the RIGHT groin and half in the LEFT groin at a maximum of 0.2 mL per intradermal injection. A target of six cycles with maximum of twelve cycles of TMZ may be given to patients enrolled before approval of protocol version 20181218 and to methylated patients enrolled after approval of protocol version 20181218, at the discretion of the treating neuro-oncologist. Unmethylated patients enrolled after approval of protocol version 20181218 will receive only one cycle of TMZ. After the completion of a patient's last TMZ cycle, vaccines will continue every 4-6 weeks for a maximum number of 20 vaccines (unless tumor progression occurs).
 
Patients will be imaged with contrast-enhanced MRI within 2 weeks (+3 days) after vaccine 3 and then approximately every 8 weeks [every 2 cycles thereafter (i.e., end of cycles 3, 5, 7, 9, 11)]. RANO criteria will be used for assessment of pseudo-progression, and patients demonstrating definitive progression will be removed from study. Any patient removed prior to immune monitoring post vaccine 3 will be replaced for immunologic endpoints. Clinical endpoint comparisons will be made amongst patients successfully randomized to adjuvant TMZ treatment arms and receiving at least one vaccine.
 
Blood for immune monitoring will be obtained:
 
• Prior to Td pre-conditioning• During vaccines 1 and 2 (just prior to Component A, 1 and 2 hours after Component A)• Prior to vaccine 3• After vaccine 3 (within 2 weeks of vaccine 3 [+ 3 days])• Prior to vaccines 4 and 6

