Statistical Analysis	
Of primary interest in this study is a comparison of the 2 arms with respect to peak immune response (ELISPOT) in the immune monitoring blood that will be collected as described in the treatment plan. The ACT II study conducted at Duke provides antibody titer data that can be used to estimate an appropriate sample size for comparison of antibody response. ELISPOT data is not available. The ACT II dataset provides peak antibody titer to EGFRvIII data for 5 patients in Arm A (treated with 5 day TMZ) and 10 patients in Arm B (treated with 21 day TMZ). Given that the distribution of peak titers in the two arms is not normally distributed, resampling methods were used to estimate the power of a comparison using a one-tailed Wilcoxon rank sum test. Each of 10000 simulations for a fixed sample size per arm involved random sampling with replacement the peak antibody data separately within arm A and B, and then computing the Wilcoxon rank sum test. The percentage of tests that was statistically significant estimated the power of the statistical test. With 2 primary endpoints, power calculations assumed a type I error rate of 0.025. With 13 evaluable patients per arm having immune monitoring done prior to vaccine 4, there is 81% power to detect a difference similar to that observed in ACT II.
 
With the goal of 26 evaluable patients (13 per arm) for the primary outcomes, a maximum of 70 patients may be consented on the main informed consent to meet this goal. With the 20190312 protocol amendment, the primary analysis dataset includes only patients who receive Component A alone (See Section 15.2). Hence, after this amendment, the study targets the accrual of 26 patients (13 per arm) who receive only Component A and are evaluable for the assessment of immunologic response.
 
Following the safety events of vaccine reactions that were initially reported on 20170407, the study was amended to investigate, in a separate

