Patients who receive more than 1 cycle of TMZ will be vaccinated in conjunction with each **subsequent** 28-day TMZ cycle for a total of 6 to 12 cycles of TMZ after RT followed by further vaccination up to 20 vaccines. Patients who receive only 1 cycle of TMZ will be vaccinated on a 28-day cycle with up to 20 vaccines. All cycles, with or without TMZ, may be given every 4 (+ 2) weeks, in order to adjust for slight delays on startup of each 28-day cycle, and the total number of cycles are given at the discretion of the treating oncologist. During vaccine (+/- TMZ) cycles, vaccinations will occur on day 23 (-1 day, + 2 days) of each cycle for each arm: (Arm 1) standard TMZ (150-200 mg/m²/day on days 1-5 of each 28-day cycle), or (Arm 2) dose-intensified TMZ (75-100 mg/m²/day on days 1-21 of each 28-day cycle). All vaccines will be given i.d. approximately 10 cm below the inguinal ligament bilaterally. A target of six cycles with a maximum of twelve cycles of TMZ may be given to patients enrolled prior to approval of protocol version 20181218 and those with MGMT/inconclusive methylation status if enrolled after approval of protocol version 20181218, at the discretion of the treating neuro-oncologist. After the completion of a patient's TMZ cycles, vaccines will continue to be administered every 4 (+ 2) weeks for a maximum of 20 vaccines (unless tumor progression occurs).

Patients will be imaged with contrast-enhanced MRI after vaccine 3 (at cycle 2 initiation visit) and then approximately every 8 weeks [every 2 cycles thereafter (i.e., end of cycles 3, 5, 7, 9, 11)]. RANO criteria [111] will be used for assessment of pseudoprogression and patients demonstrating definitive progression will be removed from study. Any patient removed prior to immune monitoring post vaccine 3 will be replaced for immunologic endpoints. Clinical endpoint comparisons will be made amongst patients randomized to adjuvant TMZ treatment arms who have received at least one vaccine.

Blood for immune monitoring will be obtained:

- Prior to Td pre-conditioning
- During vaccines 1 and 2 (just prior to Component A, 1 and 2 hours after Component A)
- Prior to vaccine 3
- After vaccine 3 (within 2 weeks of vaccine 3 [+ 3 days])
- Prior to vaccines 4 and 6
- At tumor progression (if feasible)

Patients seen by the Duke neuro-oncology team between these vaccine visits may have blood drawn for immune monitoring at the discretion of the study team.

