13.2 Enzyme-Linked Immunospot (ELISPOT) Assay

The ELISPOT assay, our primary assay to detect cellular immune responses, is a sensitive detection assay for evaluation of antigen-specific cytokine producing T-cells. The IFN- γ ELISPOT allows for the direct visualization of human γ -interferon cytokine release from a single cell, which has been widely reported to be an indicator of activation of an antigen-specific immune response. Testing will include, but not be limited to, interferon gamma detection.

On the day of testing, PBMC will be thawed quickly, washed, resuspended in R-10 medium and cell counts and viability measured by Guava Counter (Guava Technologies, Inc., Hayward, CA). Cells will then be rested overnight at 37°C, 5% CO₂, washed, and cell counts and viability measured by Guava Counter. PBMCs (250,000/well) will be stimulated overnight with synthetic peptide pp65 in Component A of the PEP-CMV vaccine. Aliquots of the peptide will be resuspended to a final concentration of 1 μ g/mL for each peptide. Each assay will include PBMC cultured with no peptide or PHA (2.5 μ g/mL, 0.25 μ g/mL) and positive and negative control PBMC for each antigen if available. PBMC are added to duplicate wells of 96-well ELISPOT assay plates coated with mouse IgG₁ anti-human IFN-

γ monoclonal antibody (MAb) will be incubated overnight at 37 °C, 5% CO₂, washed with PBS/Tween 20, incubated with biotinylated mouse IgG₁ anti-human IFN- γ MAb for 1 h at room temperature, washed with PBS, incubated with avidin-peroxidase complex for 1 h at room temperature, washed, incubated with substrate (3-amino-9-ethylcarbazole) for 4 min at room temperature and spot development stopped by distilled water rinse. Plates will be dried and shipped to Zellnet Consulting (New York, NY) for spot enumeration by automated analysis with a Zeiss KS ELISPOT system. Results will be expressed as the mean spot-forming cells (SFC)/10⁶ PBMC after subtraction of counts from cells cultured with no peptide. If a response above background is detected to the peptide, responses will be measured by polyfunctional T cell assay to the pp65 peptide and to the gB peptide depending on availability of cells.

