15.4 Analytic Methods

15.4.1 Primary Analyses

Safety: To assess the safety of PEP-CMV vaccination in combination with adjuvant TMZ, the percentage of patients with unacceptable toxicity will be estimated within each arm. All patients who received any PEP-CMV vaccine will be included in these safety analyses.

As described in Section 15.1, the vaccination treatment regimen has been modified over time due to safety issues. Hence, toxicity will be summarized for each period of study conduct as follows:

- Initial randomization period where patients were assigned to one of two TMZ regimens with both Component A and B. The 2 patients assigned to standard TMZ after randomization resumed who received both Component A and B will also be included in this summary.
- Safety Cohort Period in which all patients received standard TMZ with vaccine Component A and B
- Randomization period in which patients received at least one cycle of Component B prior to discontinuation
- Randomization period in which patients are assigned to one of two TMZ regimens and receive only vaccine Component A

Immunologic Response: The primary analysis will focus on patients who have follow-up immunologic monitoring after the 3rd vaccination and before initiation of the second TMZ/vaccine cycle. Such a patient is considered “evaluable” for the immunologic response primary analyses.

The Wilcoxon rank sum test will compare treatment groups with regard to the median peak number of T cells that secrete IFNy by ELISPOT in response to component A of PEP-CMV. Analyses will include only those patients who have an assessment of immune response after receiving 3 vaccinations.

Though the original vaccination included Component A and B, the primary immunologic analysis will focus on only those patients who received Component A alone. Additional exploratory analyses may include data from the few “evaluable” patients who received both vaccine Components A and B.

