15.4.3 Exploratory Immunologic Analyses

The following immunologic analyses will focus on patients who are evaluable for the immunologic monitoring primary analysis, i.e., patients who had immunologic monitoring conducted at baseline and prior to the second cycle of TMZ. These analyses will focus primarily upon patients who received only Component A. However, additional analyses may be conducted besides those described below.

Quality of Immune Response: The quality of the immune response will be assessed by polyfunctional flow cytometry. The analysis used here for polyfunctionality will be one that has been successful at distinguishing HIV progressors and non-progressors based on T-cell phenotype [115, 116]. All data will be background subtracted. For each measure, a lower threshold corresponding to two standard deviations above background is set to 0 based on a Poisson model essentially allowing T-cells to be designated as positive or negative for a certain phenotypic marker. The number of positive phenotypic markers post-vaccination will be calculated for each patient. The Kruskal-Wallis test will be used to compare treatment arms with respect to the number of phenotypic markers observed post-vaccination 3, as well as at vaccination 6. Additional exploratory analyses will be conducted using a Fisher's exact test that will compare treatment groups with respect to the proportion of patients with 5 positive markers, and 4 or more positive markers. Analyses similar to those described for the primary immunologic analyses will be used to examine the percentage of tetramer positive cells.

Analysis of covariance will be used to compare treatment groups with respect to the change between baseline and post-vaccination time-points in mean proliferative response and cytokine production, with baseline levels included in the model as a covariate. If assumptions of normality are not satisfied, the Kruskal-Wallis test will be used to compare treatment arms. Analyses will focus on the change between baseline and post-vaccination 3 assessments, as well as the change between baseline and vaccine 6.

Effect on Tregs: The mean levels of Tregs at baseline and at each follow-up assessment will be estimated within each treatment group. A mixed model that accounts for the correlation of repeated measurements within a patient will be used to compare treatment groups with respect to changes in Treg levels over time.

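### Must the plan list which blood draws count towards the primary peak ELISPOT?

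*Combined protocol and SAP*

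**What the plan says.** The synopsis and section 15.2 use the same words for the endpoint: "peak immune response (ELISPOT) in the immune monitoring blood that will be collected as described in the treatment plan". Section 15.4.1 compares the arms on the peak IFN-gamma ELISPOT count by Wilcoxon rank sum test and names no draw.

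The schedule referred to (synopsis; section 11.1) has draws before tetanus pre-conditioning, around vaccines 1 and 2, before vaccine 3, and within 2 weeks (+3 days) after vaccine 3. It then adds "Prior to vaccines 4 and 6", and progression if feasible. Section 11.1 also says that patients seen between vaccine visits "may have blood drawn for immune monitoring at the discretion of the study team".

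Other text bears on the window:

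- Section 15.4.1: "Analyses will include only those patients who have an assessment of immune response after receiving 3 vaccinations".
- Section 11.1: "Any patient removed prior to immune monitoring post vaccine 3 will be replaced for immunologic endpoints".
- Synopsis, power statement: "With 13 evaluable patients per arm having immune monitoring done prior to vaccine 4".
- Section 15.4.3 describes the evaluable set as "patients who had immunologic monitoring conducted at baseline and prior to the second cycle of TMZ", and places the vaccine-6 comparisons among the exploratory analyses.
- Section 13 plans to compare pre-therapy immune measures with those taken after immunisations.

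Section 13.2 reports ELISPOT counts "after subtraction of counts from cells cultured with no peptide".

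**The concern.** A maximum depends on what it is taken over. All patients are CMV seropositive (section 10.1), and the assay subtracts the no-peptide wells rather than the patient's own pre-vaccine value. An existing pp65 response could therefore be the peak. A maximum also tends to rise with the number of samples, and the draws before vaccines 4 and 6 exist only for patients still on study. If one arm stayed on longer, its peaks would be higher with no difference in vaccine response.

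The primary endpoint is also less fully specified than some lesser ones: section 13.3 lists times for Tregs, and section 15.4.3 for polyfunctional flow cytometry. With 13 patients per arm and a single test, a choice of window made after seeing the data could decide the result.

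**Working it through.** **1. Which draws can supply an ELISPOT value.** The Table 3 footnotes list ACD tubes at six scheduled times before progression: before tetanus pre-conditioning, before vaccine 2, before vaccine 3, after vaccine 3, before vaccine 4 and before vaccine 6. The draw just before vaccine 1 and the 1- and 2-hour draws list only EDTA and serum tubes, so they are unlikely sources. The literal peak is then over six draws (plus any at progression or at discretion). The narrow reading ends at the fourth.

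**2. What the text implies.** Sections 11.8, 15.2 and 15.4.1 make a patient evaluable at the post-vaccine-3 draw. Section 11.1 replaces anyone removed before it, and no rule requires a later sample. An endpoint that needs nothing after that visit is most naturally complete at that visit. These rules select patients, not values, so this is an inference, though a consistent one. The pre-conditioning sample acts as a baseline in sections 13 and 15.4.3, not as a response.

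Patients with MGMT-unmethylated tumours who have no second TMZ cycle are covered too. Sections 11.8 and 15.4.1 refer to a vaccine or TMZ cycle, section 11.1 allows cycles with or without TMZ, and section 15.2 adds an if-applicable clause.

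**3. The plan's own figure.** The stated power is 81% (13 per arm, one-tailed, 0.025). It cannot be reproduced, because the 15 ACT II titres are not given. Invented data sets matching the printed medians and ranges gave about 12% to above 99%; 81% is attainable. The point does not depend on it.

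**4. Simulation.** The documents give no ELISPOT variance, kinetics or retention, so every input here is an assumption:

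- log10 counts normal, between-patient SD 0.3, 0.5 or 0.7, within-patient SD 0.2 or 0.3;
- a rise of 0.3 or 0.5 log10 (2- or 3-fold), either immediate or building as 1/3, 2/3, 1 over the three post-vaccine draws;
- rejection when U >= 124, whose exact size at 13 v 13 is 0.0221.

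*One-sided error with no arm difference and the response held at vaccines 4 and 6:*

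| Share reaching vaccines 4/6 | Literal peak |
|---|---|
| 85%/70% in both arms | 2.0-2.3% |
| 80%/60% v 95%/85% | 2.4-3.3% |
| 60%/30% v 95%/85% | 2.6-5.4% |

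A three-draw window ending after vaccine 3 gives 2.1-2.3%. With the imbalance reversed, the literal peak gives 0.7-2.1%. If the late response is half faded, the two imbalanced rows become 2.1-2.7% and 2.1-3.3%.

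*Pre-conditioning draw.* With no rise it would be the peak of the first four draws one time in four (1/4 = 0.25). With a 2-fold rise that falls to 3-11%, and with a 3-fold rise to 0.3-5%. Including it costs 0-3 points of power. A second model, with an arm difference of 1.5 log units and a reference-arm rise of 1.0, 0, 0 or -0.5, gave larger losses: 0.715 - 0.704 = 0.011, 0.654 - 0.577 = 0.077, 0.668 - 0.569 = 0.099, and 0.625 - 0.457 = 0.168. The loss is large only if the reference arm hardly responds or falls.

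*Power, arm effect 1.2 total SD, all six draws available; literal peak minus three-draw window:*

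| Arm effect kept at vaccines 4/6 | Difference in points |
|---|---|
| 0% | -29 to -6 |
| 50% | -16 to -6 |
| 100% | 0 to +13 |
| 150% | +10 to +29 |

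The post-vaccine-3 draw alone has power 0.79-0.80 throughout. The three-draw peak has 0.81-0.89 if the effect is immediate and 0.69-0.76 if it builds, so in the second case it is 4-11 points worse than the single draw.

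**The case for a change.** The best case for amending is that it would be cheap: one sentence in section 15.4.1, no new visits or patients. The evaluability text limits patients and not values. Even the synopsis phrase about monitoring before vaccine 4 is ambiguous, since there is a scheduled draw at that point. Immune data were already being examined: sections 11.5.1, 14.1 and 14.2.1 describe data on 16 patients, with pp65-specific T-cell activation and measurable cellular responses.

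Much of this stands. The draws are nowhere listed, and they should be settled before any ELISPOT comparison by arm. The comparison reported in section 11.5.1 is of cytokines by reaction grade; the cellular findings name no assay and no comparison by arm, so that order can still be kept. A report should say that some cellular data had been seen by January 2020.

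The step from there to a required window does not stand. Three draws, one draw and the literal list each win under some kinetics. Section 9.5 reports sustained Grade 3 lymphopenia on the 21-day regimen only by cycle 3 (Figure 6 legend) or cycle 5 (text), so an arm effect that grows later cannot be ruled out; an early window would then lose most. Use of the samples before vaccines 2 and 3 for ELISPOT is also only inferred from tube types.

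**Conclusion.** No change to the plan is called for. This is an unwritten detail that the surrounding text lets an analyst fill sensibly: post-vaccine values up to the visit after vaccine 3, the same draws for every evaluable patient, with later samples treated as exploratory. Recording that choice before the arms are compared is ordinary practice.

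No bias is demonstrated. Both arms share one schedule, and with equal retention the literal reading keeps its error at 2.0-2.3%. Excess error, up to 3.3% with modest and 5.4% with large imbalance, needs an assumed difference between arms in staying on study. The pre-conditioning draw costs little if both arms respond, and the text already gives it a baseline role. The choice of window is a trade-off, from 29 points of power gained to 29 lost against the literal peak, with nothing in the documents to settle the kinetics.

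All these sizes rest on assumed variances, rises and retention. Evidence of clearly unequal retention, or of a window chosen after an arm comparison, would alter the conclusion.
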